## PASS INFORMATION

Title	An OTIS/MotherToBaby Pregnancy Registry-based observational cohort study to evaluate pregnancy and infant outcomes in individuals exposed to Boostrix as of the 1 st day of the 27 th week of gestation in the US
Protocol version identifier	219588 (EPI-PERTUSSIS-075 VS US PR)
Date of last version of protocol	Final: 23 January 2023
EU PAS (ENCEPP) register number	To be confirmed
Active substance	J07AJ52, pertussis, purified antigen, combinations with toxoids
Medicinal product	US Boostrix Vaccine
Product reference	Not applicable
Procedure number	Not applicable
Marketing authorisation holder(s)	GlaxoSmithKline (GSK) Biologicals [name] [name]
Joint PASS	No
Research question and objectives	
How do selected pregnancy and neonatal/early infant safety outcomes among pregnancies enrolled in the Organization of Teratology Information Specialists (OTIS) / MotherToBaby Pregnancy Registry who were vaccinated with the Boostrix Tdap vaccine on or after the 1st day of the 27th week of pregnancy compare to pregnancies unexposed to any Tdap vaccine during pregnancy?
 
Study Objectives:
 
 
The primary objectives of the study are to evaluate if there is an increased risk for preterm birth, small for gestational age infants, or stillbirth in pregnancies exposed to Boostrix vaccination on or after the 1st day of the 27th week of gestation when compared to a cohort of individuals unexposed to any Tdap vaccine during their pregnancy.
 

	
 
The secondary objectives of the study are to evaluate if there is an increased risk of preeclampsia/eclampsia, premature rupture of the membranes, chorioamnionitis, neonatal sepsis, neonatal death, or neonatal intensive care admission for bronchopulmonary dysplasia in pregnancies exposed to Boostrix vaccination on or after the 1st day of the 27th week of gestation when compared to a cohort of individuals unexposed to any Tdap vaccine during their pregnancy.
 

Countries of study	United States

**LIST OF ABBREVIATIONS**

ACIP	Advisory Committee on Immunization Practices
AE	Adverse Event
CA	California
CBER	Center for Biologics Evaluation and Research
CDC	Centers for Disease Control and Prevention
CI	Confidence Interval
EU	European Union
FDA	Food and Drug Administration
GA	Gestational Age
GSK	GlaxoSmithKline
HCP	Healthcare Provider
HR	Hazard Ratio
ICSR	Individual Case Safety Reports
IPW	Inverse Probability Weighting
IRB	Institutional Review Board
KPSC	Kaiser Permanente Southern California
LMP	Last Menstrual Period
MAH	Market Authorization Holder
NCHS	National Center for Health Statistics
NICU	Neonatal Intensive Care Unit
OTIS	Organization of Teratology Information Specialists
PASS	Post-Authorization Safety Studies
PROM	Premature Rupture of Membranes
PS	Propensity Score

**CONFIDENTIAL**

219588 (EPI-PERTUSSIS-075 VS US PR)

Protocol Final

PTB	Preterm Birth
RR	Relative Risk
SAP	Statistical Analysis Plan
SGA	Small for Gestational Age
SMD	Standardized Mean Differences
SOP	Standard Operating Procedure
US	United States
VAERS	Vaccine Adverse Event Reporting System

**TRADEMARK INFORMATION**

Trademarks of the GlaxoSmithKline group of companies
BOOSTRIX

Trademarks not owned by the GlaxoSmithKline group of companies

## Study Coordination.

The MAH has contracted with the University of California Research Center for the Organization of Teratology Information Specialists (OTIS)/MotherToBaby Pregnancy Studies to provide scientific leadership and to conduct the study. The OTIS/MotherToBaby Research Center will conduct the study with review and input from the MAH.

The OTIS/MotherToBaby Research Center will use a combination of previously collected data as well as newly collected data using the same standard protocol. Participants are recruited from referrals into the OTIS/MotherToBaby Research Center, some of which come through the North American OTIS/MotherToBaby network of teratogen information counseling services. The North American OTIS/MotherToBaby network is a university and health department-based group of telephone information centers serving pregnant women and health care providers throughout the US and Canada. The OTIS/MotherToBaby network receives voluntary reports of pregnancy and exposures from women and health care providers.

Principal Investigator:

[name], MPH  
University of California, San Diego  
[name]  
[name]

Phone: PPD [REDACTED]

Email: PPD [REDACTED]

#### 1.4. STUDY ADVISORY COMMITTEE

The study *Boostrix* EPI-PERTUSSIS-075 VS US PR will use an independent existing external Scientific Advisory Board under the Vaccines and Medication in Pregnancy Surveillance System (VAMPSS) that provides oversight for the study and reviews study summary data on an annual basis. Members of the Board provide advice to the Registry investigators on interpretation of the data and provide advice on strategies for the dissemination of information regarding the study.

The VAMPSS Scientific Advisory Board is managed by the American Academy of Allergy, Asthma and Immunology. The Scientific Advisory Board is comprised of membership representing specialization in maternal fetal medicine, biostatistics, vaccine epidemiology, and representation from the Centers for Disease Control, National Institutes of Health/Child Health Institute, the American Academy of Pediatrics, and a consumer representative. The Board is chaired by a designated member, and each member has one vote. A dedicated charter describes roles and responsibilities of the Board members, and members complete conflict of interest disclosures on an annual basis.

## 2. ABSTRACT

**Protocol Title:** An OTIS/MotherToBaby Pregnancy Registry-based observational cohort study to evaluate pregnancy and infant outcomes in individuals exposed to *Boostrix* as of the 1st day of the 27th week of gestation in the US.

### Rationale and Background

In June 2011, the U.S. Advisory Committee on Immunization Practices (ACIP) recommended immunization of pregnant women against pertussis (CDC, 2013). In 2012, the ACIP recommended that the Tdap vaccine be given to women during every pregnancy (preferably between 27-36 weeks' gestation). Since 2014 the maternal Tdap uptake measured by surveys conducted by the US Centers for Disease Control (CDC) has plateaued at 55% (Baïssas, 2021). Two Tdap vaccine brands are used for immunization during pregnancy in the US (CDC, 2017).

Based on current available evidence on the safety of *Boostrix* maternal immunization and the recommended gestational timing of administration of Tdap vaccine in pregnancy, there is specific interest in acquiring more safety data in a registry-type study regarding the risk of preterm birth (PTB), small for gestational age infants (SGA), stillbirth, preeclampsia/eclampsia, premature rupture of the membranes (PROM), chorioamnionitis, neonatal sepsis, neonatal death and neonatal intensive care unit (NICU) admission for bronchopulmonary dysplasia.

GSK proposes a registry study with PTB, SGA infants and stillbirth as the primary outcomes, and preeclampsia/eclampsia, PROM, chorioamnionitis, neonatal sepsis, neonatal death and NICU admission for bronchopulmonary dysplasia as the secondary outcomes. These outcomes were selected based on the current knowledge on the safety of Tdap vaccination during pregnancy, adverse events reported into the Vaccine Adverse Event Reporting System (VAERS) and the biological plausibility for the exposure timing of interest. This registry study EPI-PERTUSSIS-075 VS US PR will be established in collaboration with the OTIS/MotherToBaby Research Center, an organization with well-established measures proven to efficiently retain participants and provide more complete and meaningful data than the initial pregnancy registry established in 2005 (Kuznetsova, 2022).

Information regarding the safety of *Boostrix* in human pregnancy is essential from a public health perspective to help inform clinical practice.

### Research question and Objectives

The overall aim of the study is to determine whether the risks of pregnancy and neonatal/early infancy safety outcomes are increased among pregnant people in the Organization of Teratology Information Specialists (OTIS) / MotherToBaby Pregnancy Registry who were vaccinated with the *Boostrix* vaccine on or after the 1st day of the 27th week of pregnancy. The primary objectives of the study are to evaluate if there are increased risks for PTB, SGA infants, or stillbirth after *Boostrix* vaccination on or after the 1st day of the 27th week of pregnancy when compared to a cohort of pregnancies unexposed to any Tdap vaccine during pregnancy. The secondary objectives of the study are to evaluate the

risks of preeclampsia/eclampsia, PROM, chorioamnionitis, neonatal sepsis, neonatal death, or NICU admission for bronchopulmonary dysplasia following receipt of the *Boostrix* vaccine on or after the 1st day of the 27th week of pregnancy when compared to a cohort of pregnancies unexposed to any Tdap vaccine during pregnancy.

## **Study Design**

This is an observational cohort study of pregnancy and neonatal/early infancy outcomes in pregnancies with exposure to the *Boostrix* vaccine as well as pregnancies not exposed to a Tdap vaccine using data from the OTIS/MotherToBaby Pregnancy Registry. The incidence rates of maternal and infant outcomes for pregnancies exposed to the *Boostrix* vaccine on or after the 1st day of the 27th week of pregnancy until the end of pregnancy will be compared to those observed in a comparator cohort unexposed to any Tdap vaccine during pregnancy.

## **Population**

The study population includes pregnant women participating in the OTIS/MotherToBaby Pregnancy Registry on or after 08 March 2004 (i.e., first date of enrollment into OTIS/MotherToBaby Pregnancy Studies) who meet study inclusion and exclusion criteria. The OTIS/MotherToBaby Pregnancy Registry includes women who reside in the US. The two cohorts of participants enrolled and followed for pregnancy and infant outcomes include: 1) pregnant individuals vaccinated with *Boostrix* on or after the 1st day of the 27th week of gestation, 2) pregnant individuals unexposed to any Tdap vaccine throughout their pregnancy.

## **Variables**

Exposure will be defined as receipt of the *Boostrix* vaccine confirmed by maternal report and/or medical record, with information on the gestational timing of administration and date of vaccination captured. Pregnancy and infant outcomes of interest include PTB, stillbirth, SGA infants, preeclampsia/eclampsia, PROM, chorioamnionitis, neonatal sepsis, neonatal death and NICU admission for bronchopulmonary dysplasia.

Information on study outcomes will be obtained by maternal report and/or medical record review. Potential confounders or covariates to be collected include maternal age, race/ethnicity, pre-pregnancy body mass index, socioeconomic status, pregnancy and health history, lifestyle factors, comorbidities, maternal exposures (including medication, vaccine, vitamin/mineral, and illnesses), and prenatal tests.

## **Data Sources**

This study will use data collected as part of the OTIS/MotherToBaby Pregnancy Registry from maternal interviews, medical records (obstetric, delivery hospital, pediatric, and vaccine provider if applicable), and pregnancy exposure diary.

## Study Size and Timing

The target sample size in each of the study cohorts are as follows: 1,500 pregnant individuals exposed to *Boostrix* on or after the 1st day of the 27th week of pregnancy and 1,500 pregnant individuals not exposed to any Tdap vaccine throughout their pregnancy. Each study cohort will consist of approximately 600 participants in each cohort that have previously been enrolled in the OTIS/MotherToBaby Pregnancy Registry before the end of pregnancy, have completed their pregnancies, have met the eligibility criteria, and have sufficient medical record and exposure data to meet the study objectives. An additional 900 participants per cohort will be enrolled over four years, with enrollment occurring before the end of pregnancy, have met the eligibility criteria, and have sufficient medical record and exposure data to meet study objectives.

## Data Analysis

Demographic and other maternal characteristics will be compared between the two cohorts. The outcome analyses include:

1. comparison of proportion of PTBs among those enrolled prior to 37 weeks' gestation and resulting in a live born singleton infant between the *Boostrix*-exposed cohort and the comparison cohort by calculating hazard ratios and associated 95% confidence intervals.
2. comparison of proportion of stillbirths between the *Boostrix*-exposed cohort and the comparison cohort by calculating relative risks and associated 95% confidence intervals.
3. comparison of proportion of SGA infants ( $\leq 10^{\text{th}}$  centile for sex and gestational age) on birth weight, length, and head circumference among live born singletons between the *Boostrix*-exposed cohort and the comparison cohort by calculating relative risks and associated 95% confidence intervals.
4. comparison of proportion of preeclampsia/eclampsia diagnosed after the 1st day of the 27th week of gestation in pregnancies ending in livebirth or stillbirth between the *Boostrix*-exposed cohort and the comparison cohort by calculating relative risks and associated 95% confidence intervals.
5. comparison of proportion of cases of chorioamnionitis in pregnancies ending in livebirth or stillbirth between the *Boostrix*-exposed cohort and the comparison cohort by calculating relative risks and associated 95% confidence intervals.
6. comparison of proportion of PROM occurring after the 1st day of the 27th week of gestation in pregnancies ending in livebirth or stillbirth between the *Boostrix*-exposed cohort and the comparison cohort by calculating relative risks and associated 95% confidence intervals.
7. comparison of proportion of cases of neonatal sepsis occurring in pregnancies ending in live birth including twins or higher order multiples between the *Boostrix*-exposed cohort and the comparison cohort by calculating relative risks and associated 95% confidence intervals.

8. comparison of proportion of neonatal deaths occurring in pregnancies ending in live birth including twins or higher order multiples between the *Boostrix*-exposed cohort and the comparison cohort by calculating relative risks and associated 95% confidence intervals.
9. comparison of proportion of NICU admissions for bronchopulmonary dysplasia occurring in pregnancies ending in live birth including twins or higher order multiples between the *Boostrix*-exposed cohort and the comparison cohort by calculating relative risks and associated 95% confidence intervals.

Initial analysis will be unadjusted. Adjusted analyses will be conducted where numbers of events permit, multivariable analyses will be conducted to adjust for possible confounders.

For the *Boostrix*-exposed cohort, follow-up time with respect to the primary and secondary outcomes will start on the date of *Boostrix* vaccination, and for the comparator cohort, follow-up time will start on the 1st day of the 27th week of gestation.

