Preeclampsia / eclampsia	Secondary Outcome	Maternal report Medical record	Maternal report and medical record documentation of preeclampsia. Preeclampsia is defined as hypertension in conjunction with at least one of the following: proteinuria; thrombocytopenia; impaired liver function; renal insufficiency; pulmonary edema; or visual or cerebral disturbances. The disorder usually occurs after 20 weeks of pregnancy and worsens over time.

Variable	Role	Data Source(s)	Operational Definition
			Eclampsia is a life-threatening condition that is considered a complication of severe preeclampsia and characterized by coma and/or seizures that are unrelated to a preexisting brain condition. Onset of preeclampsia/eclampsia as an outcome for this study is defined as onset after the 1 st day of the 27 th week of gestation or Boostrix vaccination date (whichever comes later).
Premature rupture of the membranes (PROM)	Secondary Outcome	Maternal report Medical record	Maternal report and medical record documentation of premature rupture of the membranes (amniotic sac). Premature rupture of the membranes is before labor begins on or after the 1 st day of the 27 th week of gestation or date of Boostrix vaccination (whichever comes later) and prior to 37 weeks' gestation.
Chorioamnionitis	Secondary Outcome	Maternal report Medical record	Maternal report and medical record documentation of chorioamnionitis. Chorioamnionitis classified using Brighton collaboration definition ( Kachikis, 2019 ) Please refer to details in Appendix 1
Neonatal sepsis of early onset	Secondary Outcome	Maternal report Medical record	Maternal report and medical record documentation of neonatal sepsis. Sepsis defined as isolation of pathogenic species from blood or cerebrospinal fluid culture within 72 hours of birth and antibiotic treatment for at least 5 days or until death (provisional definition pending confirmation of the ability to implement extraction in medical records)
Neonatal intensive care (NICU) for bronchopulmonary dysplasia	Secondary Outcome	Maternal report Medical record	Maternal report and medical record documentation of NICU care for bronchopulmonary dysplasia. Admission to the NICU defined as admission for any number of days for diagnosis of bronchopulmonary dysplasia

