**Table 5 Summary of Exposure Window for Selected Primary and Secondary Outcomes**

Outcome	Exposure Window
Preterm Delivery	1 st day of the 27 th week of gestation to the 5 th day of the 37 th week of pregnancy
SGA	1 st day of the 27 th week of gestation to the end of the pregnancy
Chorioamnionitis	1 st day of the 27 th week of gestation to the end of the pregnancy

For the binary endpoints of **SGA and Chorioamnionitis**, the comparison will be on the proportion of events occurring after the 1st day of the 27th week of gestation or the date of *Boostrix* vaccination (whichever comes later) between the *Boostrix*-exposed cohort and the comparison cohort. A point estimate of the crude (i.e., unadjusted) relative risk (RR) of the *Boostrix*-exposed cohort versus the comparison cohort, as well as its 95% confidence interval (CI) will be computed.

Due to the observational nature of the study, the above crude estimate of RR will be further adjusted for potential confounders using a propensity score (PS) approach, if there are a sufficient number of events (to be detailed in Statistical Analysis Plan). A complete list of potential confounders will be provided in a separate table for each outcome prior to the final analysis, based on scientific knowledge including literature review. In addition, all of the following three criteria will be applied in accordance with the definition of confounders (Greenland, 1999; Xu, 2018), to identify confounders to be included in the PS model: 1) by assessing each considered variable in a logistic regression model containing exposure and the outcome to determine if inclusion of that single covariate changes the estimate of the odds ratio for exposure by 10% or more; 2) standardized mean differences (SMD) greater than 0.1; 3) association with the outcome with p-value <0.2 in the unexposed group. Care will be taken not to include those variables that are strongly associated with the exposure but only weakly associated with the outcome (Brookhart, 2006).

The confounders identified above may be used to build the PS for exposure (Rosenbaum, 2002). R package ‘twang’ or similar R package available at the time of analysis will be used for this purpose, following which SMD will be used to check the balance of the covariates between the cohorts.

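### The abstract's event windows for preeclampsia/eclampsia and PROM conflict with Table 1 and the follow-up rule, and neither rule compares women over matching time at risk

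*Protocol*

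**What the plan says.** Three places in the protocol set the time window for these two secondary outcomes. Several quotations below stop at an ordinal; the text continues to the 1st day of the 27th week of gestation.

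- **Section 2 (Abstract), Data Analysis, items 4 and 6.** Item 4 is a "comparison of proportion of preeclampsia/eclampsia diagnosed after the 1"; item 6 is a "comparison of proportion of PROM occurring after the 1". Both apply to both cohorts and neither mentions the vaccination date. The denominator is all pregnancies that end in a live birth or stillbirth: "week of gestation in pregnancies ending in livebirth or stillbirth between the" two cohorts.
- **Same section, closing paragraph.** For the exposed cohort, "follow-up time with respect to the primary and secondary outcomes will start on the date of" vaccination; "for the comparator cohort, follow-up time will start on the 1"st day of week 27.
- **Table 1 (Section 7.3.2).** "Onset of preeclampsia/eclampsia as an outcome for this study is defined as onset after the 1"st day of week 27 or the vaccination date, whichever is later. PROM has the same start and also an upper limit: "vaccination (whichever comes later) and prior to 37 weeks' gestation".

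Section 7.7.1 does not settle the matter. For SGA and chorioamnionitis it says "the comparison will be on the proportion of events occurring after the 1"st day of week 27 or the vaccination date, whichever is later, and it treats preterm delivery separately. It names neither preeclampsia/eclampsia nor PROM.

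**The concern.** Two analysts working from this protocol could count different exposed cases. Take a woman vaccinated in week 33 whose preeclampsia began in week 30. Item 4 makes her an exposed case. Table 1 makes her a non-case who is still in the denominator. A comparator with onset in week 30 is a case under both rules.

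Neither treatment of the vaccinated woman is sound, because she was no longer at risk when her follow-up began. The list mixes pre-dose events into the exposed risk and dilutes a true effect. Table 1 removes those events from the exposed cohort only, while comparators are still counted from week 27. In a safety study that pushes the relative risk downward and can hide harm.

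For PROM there is a second mismatch. Item 6 has no upper limit, so rupture before labor at 37 weeks or later counts under the list and not under Table 1, in both cohorts.

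**Working it through.** The protocol states no rate, power or detectable effect specific to either outcome, so there is no figure of its own to reproduce. The check is a comparison of texts, followed by an illustration of size.

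**Texts side by side**

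| Rule | Exposed window opens | Comparator window opens | PROM upper limit |
|---|---|---|---|
| Abstract items 4 and 6 | week 27, day 1 | week 27, day 1 | none |
| Table 1 | later of week 27, day 1 and vaccination | week 27, day 1 | before 37 weeks |
| Abstract follow-up paragraph | vaccination | week 27, day 1 | not stated |

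Nothing removes women already affected when their window opens. In Section 7.2.1 the only exclusion specific to Cohort 1 is earlier inclusion in the study.

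**Inputs**
- Cohort size N = 1,500 (Section 7.5).
- Event rate r: Section 7.5 expects the secondary endpoints without a power figure to occur in fewer than 1-2% of comparators.
- f, the share of exposed women's onsets after week 27 that fall before the dose: not in the protocol, assumed 2-20%.

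The upper part of that range can be motivated as follows. Suppose onsets run over weeks 26 to 40 with density growing as e^(gt), and doses are spread evenly over weeks 27 to 36. Then f = [(e^(10g) − e^g)/(9g) − 1] / (e^(14g) − 1). This gives 0.20 for g = 0.15 per week and 0.07 for g = 0.35. Doses clustered early in the window lower f; 2% is taken as the low end.

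**Cases that change status**
- Events = N × r: 1,500 × 0.01 = 15 and 1,500 × 0.02 = 30.
- Switching cases = N × r × f: from 15 × 0.02 = 0.3 to 30 × 0.20 = 6.
- Exposed risk under the list divided by exposed risk under Table 1 = 1/(1 − f): 1.02 to 1.25, whatever the event rate.

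**RR with no true effect**, dose timing unrelated to onset
- List: 1.
- Table 1 with comparators counted from week 27: 1 − f, that is 0.98 to 0.80.
- Removing affected women from the exposed denominator alone hardly helps: at most 6 of 1,500 leave (0.4%), which raises the RR by a factor of about 1.004.

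**RR when the true post-dose RR is 1.5**
- List: f × 1 + (1 − f) × 1.5 = 1 + 0.5(1 − f): 1.49 to 1.40.
- Table 1: 1.5 × (1 − f): 1.47 to 1.20.

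If f were as high as 30%, 9 of 30 cases would switch and the null RR under Table 1 would be 0.70.

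**The case against.** The best defence is that the abstract list is a summary and Table 1 governs. Section 7.6.1 says outcomes are coded by the protocol's definitions, and those are in Table 1. The abstract's own follow-up paragraph covers all secondary outcomes. Items 2 and 5 of the list give no onset window at all and plainly rely on later text. Prevalent cases could be handled in the SAP, since Section 7.7.3 says each outcome has its own set of subjects.

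Much of this stands. A reader might infer that items 4 and 6 are the only analysis statement for these outcomes. They are not: the follow-up paragraph, the coding rule and the preeclampsia sensitivity analysis in Section 7.7.2 also bear on them. A reader might also infer that pre-dose events will be charged to the vaccine. That follows only if the list overrides Table 1, and nothing in the protocol says that it does.

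What remains is this. Items 2 and 5 are silent, whereas items 4 and 6 state a window, and it is a different one. Section 7.7.1 restates the later-of rule for SGA, chorioamnionitis and preterm delivery but not here, so the list holds the only outcome-specific windows in the analysis text. Reading Table 1 as governing also does not cure the problem: it keeps affected women as event-free and leaves the windows unequal. The SAP may refine definitions, but the unequal start of follow-up is fixed in the protocol itself.

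**Conclusion.** The conflict is real and should be resolved before any analysis. It is a contradiction about which events count, together with a start-of-follow-up problem that simple harmonisation with Table 1 would leave in place.

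The absolute size is modest: about 0.3 to 6 exposed cases at the protocol's expected rates. The count scales with the rate; the relative distortion does not. For f of 2-20%, the two rules differ by a factor of 1.02 to 1.25 in exposed risk, and the Table 1 rule pulls a null RR to between 0.98 and 0.80.

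These figures rest on an assumed f and on dose timing that is unrelated to onset. Women who deliver before a planned dose cannot enter Cohort 1, which would lower f, particularly for PROM. The effect of the missing 37-week limit is not included and cannot be sized from the protocol.

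**What to change.** 1. Reword abstract items 4 and 6 to the Table 1 definitions, including the upper limit for PROM, and name both outcomes in Section 7.7.1.
2. Restrict each analysis to women event-free for that outcome at their own start of follow-up, in numerator and denominator, in both cohorts.
3. Make the windows comparable, in one of two ways:
   - Time-dependent vaccine exposure with delayed entry, as Section 7.7.1 already plans for preterm delivery. Time between entry and the dose is then unexposed, and an onset in it is an unexposed event. The follow-up paragraph and the Table 1 clause must be worded to allow this, and the estimate becomes a hazard ratio.
   - Comparator start dates matched to the gestational age at vaccination, among comparators still pregnant and event-free at that point. This keeps the relative risk.

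The cost is a little more analysis work and a few women leaving each denominator. Vaccination dates are already collected under Section 7.3.1, and Table 1 already presupposes a date of onset.
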